8.4. Other Safety Analyses

The analyses of non-laboratory safety test results including ECGs and vital signs will be based on GSK Core Data Standards, unless otherwise specified. The details of the planned displays are presented in [Appendix 14: List of Data Displays](#).

ECG values of potential clinical importance are defined as a QTc of > 500 msec or increase from baseline in QTc \geq 60 msec.

9. PHARMACOKINETIC ANALYSES

The GSK Division of Clinical Pharmacology Modelling and Simulation (CPMS) will be responsible for the PK analysis of CAB. The Division of Clinical Pharmacology and Pharmacometrics at Janssen Research and Development will be responsible for conduct or oversight of the PK analysis for RPV.

9.1. Endpoint / Variables

9.1.1. Drug Concentration Measures

Refer to [Appendix 5](#) Data Display Standards & Handling Conventions (Section [15.5.3](#) Reporting Standards for Pharmacokinetic)

9.2. Overview of Planned Analyses

[Table 5](#) provides an overview of the planned analyses with full details being presented in [Appendix 14](#): List of Data Displays. All PK displays will be based on the PK Population, unless otherwise specified.

Table 5 Overview of Planned Pharmacokinetic Analyses

	Stats Analysis			Summary		Individual	
	T	F	L	T	F	F	L
Pharmacokinetic ^[5]							
Plasma CAB concentration by visit				Y ^{[1][2]}	Y ^{[1][3][4]}	Y ^[3]	Y
Plasma RPV concentration by visit				Y ^{[1][2]}	Y ^{[1][3][4]}	Y ^[3]	Y
Steady state concentration	Y						

NOTES:

- T = Table, F = Figure, L = Listings, Y = Display generated.
 - Stats Analysis = Represents TFL related to any formal statistical analyses (i.e. modelling) conducted.
 - Summary = Represents TF related to any summaries (i.e. descriptive statistics) of the observed raw data.
 - Individual = Represents FL related to any displays of individual participant observed raw data.
 - Unless otherwise specified, all displays for evaluable concentrations except for individual displays will be presented by both overall and the rederived randomization strata.
1. For both 'all' concentration and the 'evaluable' concentration. The evaluable concentration is derived from samples collected within pre-specified Time window (Section [15.6.5](#))
 2. For both 'untransformed' and 'log-transformed' statistics.
 3. The plots will be produced for the untransformed scale (i.e., a linear plot) and the log transformed scale (i.e., log-linear plot), separately.
 4. Separate plots will be produced for Mean (SD) and Median concentration.
 5. Standard summary statistics for concentration data will be calculated (i.e., mean, standard deviation, coefficient of variation, median, minimum and maximum). For Logarithmically transformed data, the summary statistics (i.e. geometric mean, between subject coefficient of variation, 95% confidence interval for the geometric mean and standard deviation) will also be calculated.

9.3. Statistical Analyses / Methods

Planned PK statistical analysis
Steady State Concentration
Endpoints

 log_e-transformation of the Trough/Pre-dose evaluable plasma concentrations (CAB/RPV) on Week 16-48 (i.e. Weeks 16, 24, 32, 40 and 48) for participants receiving Q8W study treatment
Covariates

 Study Week
Data Handling

 All data remains as is (observed).
Model Specification

 A mixed effects ANOVA model will be fitted for each rederived randomization stratum [prior exposure to CAB+RPV (0 weeks, 1-24 weeks, >24 weeks)] with Study Week (continuous variable) as a fixed effect and subject as a random effect for each analysis separately. The Kenward & Roger (KR) degrees of freedom approach will be used. The coefficient for the slope of the week effect on the log_e-scale will be used to evaluate steady state for each drug (CAB/RPV). The 90% confidence intervals for the slope for each treatment will be calculated. If it does not appear that steady-state has been demonstrated, early weeks (e.g. Week 16, 24, etc...) results will be dropped and the analysis repeated.
Model Checking & Diagnostics

 The steady state will be claimed (the coefficient for the slope of the week effect on the (natural) log scale was close to 0 or the 90% CI for the slope estimate included zero. If steady-state is not demonstrated, concentrations from early weeks (e.g. Week 16, 20, 24, etc...) dropped in sequence and the analysis repeated until either steady state is shown or only two timepoints remain.
Model Results Presentation

 The coefficient for the slope of the week effect on the log_e-scale, its standard error and 90% interval will be presented for each rederived randomization stratum.

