1. INTRODUCTION

The purpose of this reporting and analysis plan (RAP) is to describe the analyses to be included in the Clinical Study Report for Protocol:

Revision Chronology:		
2017N326521_00	17-JUL-2017	Original
2017N326521_01	14-SEP-2017	The primary purpose of protocol amendment # 1 is to revise the study sample size to randomize approximately 1020 participants including 510 participants per arm based on a non-inferiority margin of 4% between the CAB LA + RPV LA Q8W and Q4W arms.
2017N326521_02	03-Jul-2018	
The primary reasons for amendment #2 are to:
 
 • Add the additional interim analysis of data when all subjects have completed the Week 24 visit, with the intent of expediting the submission of study results to Health Authorities; • Change the objective for assessing the preference for CAB LA + RPV LA every 8 weeks or CAB LA + RPV LA every 4 weeks LA compared to oral antiretroviral (ARV) and the preference for CAB LA+ RPV LA every 8 weeks compared to CAB LA + RPV LA every 4 weeks from an exploratory objective to a secondary objective. A change to the supporting version of the Preference questionnaire administered to participants at Week 48 (or withdrawal) is also acknowledged; • Add revisions and clarifications for the administration of health outcomes questionnaires; • Extend exclusion criterion #28 to also exclude hereditary coagulation and platelet disorders such as haemophilia or Von Willebrand Disease; • Update exclusion criterion #11 to indicate that CD4+ counts <200 cells/μL are not exclusionary; • Offer clarification that withdrawal assessments will be performed for any participant who withdraws prematurely from the Maintenance or Extension Phase. Additional guidance for participants withdrawing at Week 52 or Week 100 has been added; • Offer guidance to monitor medications that are dependent on OAT1 and OAT3 transport upon concomitant exposure with CAB; • Specify that 2-hour post-dose ECG should be performed at Day 1 and Week 48 only for participants receiving CAB LA + RPV LA as it is not required to perform 2-hour post-dose ECG for those receiving oral CAB + RPV at Day 1;

Revision Chronology:		

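### Section 9.3 accepts steady state when the slope is merely not significant, and repeats the test on ever less data, so imprecision can earn the claim

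*SAP*

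**What the plan says.** SAP Section 9.3 analyses log-transformed evaluable pre-dose concentrations of CAB and of RPV in the Q8W arm at "Weeks 16, 24, 32, 40 and 48". "A mixed effects ANOVA model will be fitted for each rederived randomization stratum", "with Study Week (continuous variable) as a fixed effect and subject as a random effect". The slope and its 90% CI decide the question.

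Under Model Checking & Diagnostics, steady state is claimed if the slope "was close to 0 or the 90% CI for the slope estimate included zero". Otherwise the concentrations from early weeks are "dropped in sequence and the analysis repeated until either steady state is shown or only two timepoints remain".

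The section gives no numerical limit for closeness to zero, no equivalence margin, no minimum precision and no allowance for repeated fits. The slope, its standard error and its 90% interval are to be presented by stratum; this is Table 4.7 in the list of displays (Section 15.14.5.6).

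**The concern.** A 90% CI that includes zero shows only that a zero slope was not rejected at the two-sided 10% level. It does not show that the slope is small. Used as an acceptance rule it runs the wrong way: the fewer the participants or the noisier the assay, the wider the interval and the easier the claim.

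The refitting rule adds to this. If the trough rises at a constant rate, removing Week 16, then 24, then 32 leaves the true per-week slope unchanged and only discards precision. The alternative route, a slope near zero with no number attached, can be judged after the data are seen.

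At stake is whether a table from a dosing-interval trial says that Q8W troughs have stabilised when they are still rising. The rule is applied separately to two drugs in three prior-exposure strata, so there are up to six such statements.

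**Working it through.** The SAP states no power, error rate or margin for this analysis, so there is no figure of its own to reproduce.

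**Inputs from the SAP (Section 9.3).** Five visits at Weeks 16, 24, 32, 40 and 48; a linear week effect with a random subject effect; a two-sided 90% CI; at most four fits (5, 4, 3 and 2 visits). The Q8W arm has about 510 participants (Section 1), which is the ceiling for any stratum.

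**Assumed, because the SAP does not give them.** Complete data; within-subject SD of log trough 0.3 (0.2 to 0.5 also tried); stratum size 30 to 300; a log-linear rise that never plateaus. Acceptance by the undefined near-zero route is left out; it could only raise the rates.

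**Loss of precision, from the visit schedule alone.** With complete data, SE(slope) = SD / √(n × Sxx), where Sxx is the sum of squared deviations of the weeks from their mean.
- Five visits, mean 32: Sxx = 16² + 8² + 0² + 8² + 16² = 640.
- Weeks 40 and 48, mean 44: Sxx = 4² + 4² = 32.
- Ratio of interval widths: √(640/32) = √20 = 4.47. It needs no SD or stratum size.

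**One case by hand.** A 25% rise over 32 weeks is a slope of ln(1.25)/32 = 0.2231/32 = 0.00697 per week. Take SD 0.3 and n=30.
- Five visits: SE = 0.3/√(30 × 640) = 0.00217; slope/SE = 3.22; P(CI includes zero) ≈ Φ(1.645 − 3.22) ≈ 6%.
- Last two visits: SE = 0.3/√(30 × 32) = 0.00968; slope/SE = 0.72; P ≈ Φ(0.925) − Φ(−2.365) ≈ 81%.

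**Whole sequence, simulated.** Steady state is declared at the first fit whose 90% CI includes zero. Constant 25% rise, SD 0.3:

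| n in stratum | Declared steady, full sequence |
|---|---|
| 30 | 88% |
| 60 | 77% |
| 130 | 57% |
| 300 | 27% |

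On all five visits alone the rate is 0 to 7% across these sizes, so nearly all these declarations come from refitting on fewer visits.

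**Sensitivity, full sequence.**
- 20% rise, SD 0.3: 92% at n=30, 75% at n=100, 42% at n=300.
- 20% rise, n=100: 53% at SD 0.2, 85% at SD 0.4.
- 30% rise, n=300, SD 0.3: 15%.
- Flat trough: 90% at the first fit, as expected, and 99.6% after all four.

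**The case against.** The strongest defence is that removing early weeks is how one dates the onset of a plateau, and that stands. If the trough rises 30% from Week 16 to Week 32 and is then flat, the plan's sequence declares steady state in about 98% of trials, whereas a single Week 16 to 48 fit held to 0.80–1.25 does so in 1% or less (n=60 to 300). The fault lies in the acceptance criterion, not in the refitting as such.

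A reader might infer that a rising trough will usually be called stable. The documents do not support that: it depends on stratum size, SD and trend, none of which the SAP gives, and at n=300 a 25% or 30% rise is more often not declared stable. Nor does the sequence run until it succeeds; it stops at two timepoints.

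A reader might also infer that a trivial slope in a large stratum would be called non-steady. At the first fit it often would be: for a 5% rise at n=300 and SD 0.3 the interval includes zero in only 28% of trials. After the full sequence, however, 94% are declared steady.

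An equivalence rule also accepts rises inside its limit. With 0.80–1.25 on all five visits, a 20% rise at n=300 and SD 0.3 passes in 58% of trials, against 42% under the plan. The rate of about 5% for a 25% rise follows from that rise lying exactly on the limit. The gain is a stated limit with a controlled error at it, not rejection of every rise.

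Finally, steady state is not a listed objective or endpoint in Section 2.2. Population PK is planned separately, the PK/PD efficacy models use Week 8 troughs, and by-visit concentrations are tabulated and plotted by stratum. With the slope and its interval reported, a careful reader can see imprecision. This limits the consequence but does not make the pre-specified claim valid.

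**Conclusion.** The point holds as a defect in the acceptance rule. The plan treats a non-significant slope as evidence of stability, offers an alternative with no number, and repeats the test while precision falls by a factor of up to 4.47. That factor follows from the visit schedule alone. The rates of 88%, 77%, 57% and 27% for a constant 25% rise rest on an assumed SD of 0.3, assumed stratum sizes, complete data and a trend that never plateaus. What does not depend on those choices is the direction: other things equal, less data makes the claim easier.

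It would go too far to read this as undermining the trial's PK programme or its efficacy conclusions. The effect is confined to the steady-state statement in Table 4.7.

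**What to change.** Replace both acceptance criteria in Section 9.3 with a pre-specified equivalence limit on the per-week slope, and claim steady state only if the whole 90% CI lies inside it. One possibility is that the 90% CI for exp(32 × slope), the model-based Week 48 to Week 16 trough ratio, lies within 0.80–1.25. Those limits are not in the SAP, and the sponsor may justify others.

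Sequential removal of early weeks may stay to date a plateau, with the same per-week limit for every window. The limit should not be rescaled to the shorter window, since that would loosen it as data are discarded. State that up to four fits are made: with a 5% error per fit for a slope on the limit, the chance of at least one false claim is at most 4 × 5% = 20%.

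While editing, align the examples of dropped weeks (Week 20 is not an analysed visit) and the reference to each treatment (only Q8W is analysed).

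The cost is SAP wording; model and data are unchanged. The downside is that small strata or short windows may fail to demonstrate steady state. On all five visits with 0.80–1.25, a flat trough passes in 88% of trials at n=30 and 99% at n=50 (SD 0.3), but in 56% and 86% at SD 0.4. With Weeks 40 and 48 only and SD 0.3, the expected interval half-width, expressed as a 32-week rise, is 25.6% at n=150. At that width no estimate could pass; at n=300 it is 17.5% and a pass is possible.

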10. POPULATION PHARMACOKINETIC ANALYSES

The Population PK analyses will be described under a separate Population-PK Reporting and Analysis Plans for CAB LA and RPV LA

11. PHARMACOKINETIC / PHARMACODYNAMIC ANALYSES

The primary goal of this analysis is to characterize the pharmacokinetic / pharmacodynamic relationship of CAB/RPV administered in participants with HIV-1-infection who are virologically suppressed. The influence of subject demographics and

baseline characteristics and additional subgroups/covariates in this population will be investigated.

11.1. Overview of Planned Analyses

Table 6 provides an overview of the planned analyses with full details being presented in Appendix 14: List of Data Displays. All PK displays will be based on the PK Population, unless otherwise specified.

Table 6 Overview of Planned Pharmacokinetic / Pharmacodynamic Analyses

	Stats Analysis			Summary		Individual	
	T	F	L	T	F	F	L
CAB/RPV Week 8 concentrations by snapshot 'HIV-1 RNA \geq 50 c/mL' (Yes vs. No) for participants without prior exposure to CAB+RPV				Y	Y		
Analysis of snapshot 'HIV-1 RNA \geq 50 c/mL' at Week 48 by Week 8 trough concentration, and subgroup ^[1] – univariable analysis /multivariable analysis for participants without prior exposure to CAB+RPV	Y						
Individual CAB/RPV concentration-time profiles for participants with snapshot 'HIV-1 RNA \geq 50 c/mL' at Week 48 or 96					Y		
Maximum change from baseline in ALT/Total Bilirubin versus last trough CAB/RPV concentrations ^[2]					Y		
Maximum toxicity grades of most frequently reported study drug ISR AEs ^[3] versus last trough CAB/RPV PK concentrations ^[2]					Y		

NOTES:

- T = Table, F = Figure, L = Listings, Y = Display generated.
 - Stats Analysis = Represents TFL related to any formal statistical analyses (i.e. modelling) conducted.
 - Summary = Represents TF related to any summaries (i.e. descriptive statistics) of the observed raw data.
 - Individual = Represents FL related to any displays of individual participant observed raw data.
1. Refer to Section 11.2.
 2. Display by rederived randomization strata, i.e. prior exposure to CAB+RPV (0, 1-24, >24 weeks) derived based on eCRF.
 3. Most frequently reported study drug ISR AEs are those top 5 in incidence in either treatment arm (i.e. Q8W or Q4W arm).

11.2. Statistical Analyses / Methods

PK/PD Efficacy Analysis for Participants without Prior Exposure to CAB+RPV
Endpoints

 • Snapshot 'HIV-1 RNA \geq50 c/mL' at Week 48 (or W96)

Covariates

 Treatment, demographic and baseline characteristics except for country and Prior Exposure to CAB+RPV (0, ≥ 1 weeks), and additional subgroup/covariates for PK/PD efficacy analysis - see derivation details in Section 5.4.2.
Data Handling

 All data remains as is (observed).
Model Specification

 Logistic regression will be used to exam the correlation between the endpoint (Snapshot 'HIV-1 RNA≥ 50 c/mL') at Week 48 and the covariates/subgroups. This logistic regression analysis will be performed for each covariate or subgroup, separately (univariable analysis), and will also be performed with one multivariable analysis using Backward stepwise selection approach to identify the covariates/subgroups potentially affecting virologic response.
Model Checking & Diagnostics

 For the multivariable analysis, a logistic regression model that best predicts the dependent variable (i.e. snapshot 'HIV-1 RNA≥ 50 c/mL') from the independent variables (i.e. covariates/factors with $P < 0.15$ from univariable analysis) will be determined using the backward stepwise selecting approach. Week 8 trough PK concentration will be logarithmically transformed with base of 2 (i.e. one-unit increase of the point estimate of \log_2 PK concentration is equivalent to 'doubling the concentration' in the original value). The analysis will start with all covariates in the model and remove a covariate with the largest p-value (i.e. the least statistically significant) each time and continue until the stopping rule is reached when all remaining covariates have p-value $< 15\%$. If problems with model convergence occur due to zero event counts or complete/quasi-complete separation, then alternative methods such as exact logistic regression may be used.
Model Results Presentation

 The odds ratio, 95% confidence interval, and p-value will be presented.

12. HEALTH OUTCOMES ANALYSES

12.1. Endpoint / Variables

- Preference between injections of LA HIV treatment and daily oral HIV treatment at Week 48
- Preference between LA injection every 8 weeks and LA injection every 4 weeks at Week 48 (Q8W arm only)
- Change from baseline in total "treatment satisfaction" score, and individual item scores of the HIV Treatment Satisfaction Status Questionnaire (HIVTSQs) at Weeks 24 and 48
- Change from baseline in life satisfaction, HIV medication, and disclosure worries using HIV/AIDS Targeted Quality of Life (HAT-QoL) at Weeks 24 and 48

- Change in treatment satisfaction over time using the HIV Treatment Satisfaction Change (HIVTSQc) questionnaire at Week 48
- Change from Week 8 in Dimension Scores and individual item scores assessing pain during injection, anxiety before and after injection, willingness to be injected in the future and overall satisfaction with mode of administration over time using Perception of Injection (PIN) questionnaire at Weeks 24 and 48
- Change from baseline in treatment acceptance using ACCEPT at Weeks 24 and 48
- Reasons for continuation of receiving injectable HIV treatment at Baseline (Day 1) visit. This is an exploratory endpoint.
- Reasons for switching to injectable HIV treatment at Baseline (Day 1) visit. This is an exploratory endpoint.

12.2. Summary Measure

Mean treatment difference (Q8W – Q4W) at visits of interest, except for Preference between LA injection every 8 weeks and LA injection every 4 weeks at Week 48.

12.3. Population of Interest

The health outcomes analyses will mainly be based on the Intent-to-Treat Exposed population, unless otherwise specified.

Analysis of Reason for continuation will be based on a subset of the Intent-to-Treat Exposed population who were randomized to Q4W arm in ATLAS (i.e. ATLAS Q4W population).

Analysis of Reason for switch will be based on a subset of Intent-to-Treat Exposed population who either were randomized to SOC arm in ATLAS or did not participate in ATLAS study (i.e. SOC population).

12.4. Strategy for Intercurrent (Post-Randomization) Events

If a participant discontinues treatment prior to the timepoint of interest such that there is no evaluable assessment for the timepoint of interest, the data will be computed or imputed (see Section 15.6.6).

12.5. Statistical Analyses / Methods

Details of the planned displays are provided in [Appendix 14](#): List of Data Displays and will be based on GSK Data Standards and statistical principles.

Unless otherwise specified, endpoints / variables defined in Section 12.1 will be summarised using descriptive statistics, graphically presented (where appropriate) and listed.

12.5.1. Statistical Methodology Specification

Statistical Analyses
Endpoints

 • Change from Baseline in 
 ○ HIVTSQs total treatment satisfaction score at Weeks 24 and 48 ○ ACCEPT general acceptance score at Weeks 24 and 48 ○ HAT-QoL (Life satisfaction, HIV medications, disclosure worries) at Weeks 24 and 48 • Change from Week 8 in PIN Domain Scores (CCI [REDACTED], and CCI [REDACTED]) and Individual Items Scores (CCI [REDACTED], CCI [REDACTED]) at Weeks 24 and 48
Model Specification

 • The analysis for HIVTSQs, ACCEPT and HAT-QoL will be performed for subjects with and without prior exposure to CAB+RPV separately. 
 ○ For subjects without prior exposure to CAB+RPV, an analysis of covariance (ANCOVA) model will be used at each visit during the maintenance phase with covariates: treatment, age (<50, ≥ 50 years old), sex at birth, race (i.e. white, non-white) and baseline score value for other endpoints (as a continuous variable). ○ For subjects with prior exposure to CAB+RPV, an analysis of covariance (ANCOVA) model will be used at each visit during the maintenance phase with covariates: treatment, age (<50, ≥ 50 years old), prior exposure to CAB+RPV (i.e. 1 to 24 weeks, >24 weeks), sex at birth, race (i.e. white, non-white) and baseline score value (as a continuous variable). • For PIN, an analysis of covariance (ANCOVA) model will be used at each visit during the maintenance phase with covariates: treatment, age (<50, ≥ 50 years old), prior exposure to CAB+RPV (i.e. 0 weeks, 1 to 24 weeks, >24 weeks), sex at birth, race (i.e. white, non-white), and Week 8 score value (as a continuous variable). • Adjusted point estimates will be derived as LSMEANS using the observed margins (OM) option within PROC MIXED in SAS. • The superiority testing of Q8W compared to Q4W with respect to change from baseline in HIVTSQs total score at Week 48 will be performed using the fixed sequence procedure to control for the type I error rate at the nominal level of 5%. If the superiority testing within subjects without prior exposure to CAB+RPV demonstrates Q8W is superior to Q4W in change from baseline in HIVTSQs total score at Week 48 at two-sided 5% level of significance, the superiority testing at the same level of significance (i.e. two-sided 5%) within subjects with prior exposure to CAB+RPV will be followed. No adjustment for multiplicity will be applied for other tests as they will be considered supportive. • Interactions between treatment and each of the covariates will not be assessed unless the exploratory subgroup analyses on the primary endpoint highlights significant interactions. In this situation, the interaction(s) of interest will be assessed and, if necessary, results will be reported in the clinical study report. Interactions between treatment and the baseline score will be investigated but not included in the model. If interactions are found to be significant ($p < 0.10$), results may be presented separately by subgroup.
Dataset

 • LOCF dataset will be used.
Model Results Presentation

Statistical Analyses

 Adjusted treatment difference (Q8W – Q4W), its 95% CI and the associated p-value. The interaction between treatment and the baseline score will be included in a footnote. Plots of adjusted mean change from baseline (95% CI) for each treatment group, and the adjusted mean difference (95%CI) between the two treatment arms from the model will be generated across visit.

Statistical Analyses
HIVTSQc

 Total Treatment Satisfaction Score (Change) at Week 48
Model Specification

 An analysis of variance (ANOVA) model will be used with covariates: treatment, age (<50, ≥ 50 years old), prior exposure to CAB+RPV (i.e. 0 weeks, 1 to 24 weeks, >24 weeks), sex at birth and race (i.e. white, non-white). Adjusted point estimates will be derived as LSMEANS using the observed margins (OM) option within PROC MIXED in SAS. Interactions between treatment and each of the covariates will not be assessed unless the exploratory subgroup analyses on the primary endpoint highlights significant interactions. In this situation, the interaction(s) of interest will be assessed and, if necessary, results will be reported in the clinical study report. If interactions are found to be significant (p<0.10), results may be presented separately by subgroup. No adjustment for multiplicity will be applied as these analyses will be considered supportive.
Dataset
The observed case (OC) dataset uses only the data that is available at Week 48, with no imputation for missing values.
Model Results Presentation
Adjusted means, 95% CI, and associated p-value will be presented for the treatment difference (Q8W – Q4W).

Statistical Analyses
PIN

 Change from Week 8 in the PIN acceptance score at Week 24 and Week 48
Statistical Test

 The Wilcoxon Signed-Rank Test will be used to evaluate whether the change from Week 8 to Week 24 and to Week 48, respectively, is statistically different than zero based on a two-sided p<0.05. Separate tests will be performed for the change from Week 8 to Week 24 and for the change from Week 8 to Week 48.
Dataset

 LOCF dataset will be used
Results Presentation

 Summary statistics at each timepoint (Week 8, Week 24 and W48) and p-value for each comparison between scores at Week 24/48 with scores at Week 8.

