5.2. Baseline Definitions

For all endpoints (except as noted in baseline definitions) the baseline value will be the latest pre-treatment (see [Table 8](#)) assessment with a non-missing value, including those from unscheduled visits. 'Pre-treatment' here refers to prior to the study treatment (i.e. CAB and/or RPV) in this study.

Electrocardiograms (ECGs) are to be performed in triplicate on Day 1 visit. The baseline value for an ECG parameter will be the mean of the last pre-treatment set of assessments from the same date, so long as at least one of the triplicate assessments is available.

Unless otherwise stated, if baseline data is missing no derivation will be performed and baseline will be set to missing.

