15.3.4. Assessment Window for Health Outcome Data

15.3.4.1. PIN / HAT-QoL / HIVTSQs / HIVTSQc / ACCEPT / Preference

PIN, HAT-QoL, HIVTSQs, HIVTSQc, ACCEPT and Preference questionnaire assessments will be assigned to analysis visits as follows:

1. Baseline will be defined as last available recorded value up to and including the Maintenance treatment start date (expected to be collected at Day 1). Baseline is not applicable for PIN, HIVTSQc and Preference assessments.
2. For post-baseline visits, if the nominal visit identifier as captured in the source dataset corresponds to a scheduled collection per the Time and Events Schedule (see Section 15.2 and [Table 12](#)) and the assessment is collected in the Maintenance Phase (per [Table 14](#)), then the nominal visit identifier will be kept as the analysis visit.
3. For post-baseline visits, if the nominal visit identifier is unscheduled or withdrawal, then the following procedure will be used:
 - a) Assign the assessment to a study phase according to [Table 14](#). Proceed to step b if the assessment is assigned to the Maintenance Phase.
 - b) Identify the ‘last nominal visit’ with the HO assessment performed prior to the unscheduled/withdrawal visit to be slotted.
 - c) The unscheduled/withdrawal visit will be slotted to the planned nominal visit subsequent to the ‘last nominal visit’. If the ‘last nominal visits’ does not exist (e.g. no records originate from a planned nominal visit), then the unscheduled/withdrawal visit will be slot to the first planned nominal visit after Day 1.

Example 1, for HATQoL, the planned nominal visits are Day 1, Week 24, and 48. If a participant has the ‘last nominal visit’ (with HATQoL assessment) at Week 24 prior to withdrawal at Week 36, the withdrawal assessment will be slotted to the subsequent planned nominal visit of Week 48.

Example 2, for HATQoL, if there is unscheduled visit between Week 24 and Week 48. This unscheduled visit will be slotted to Week 48 per the rule. In this case, there are two assessments with analysis visit equal to Week 48 (i.e. the slotted value and the value at

original nominal week 48 visit). The original nominal value will be selected for summary per the rule below for multiple records—see Section 15.3.6.

Table 12 Planned Nominal Visit of Health Outcome Data

Questionnaire	Day 1	Week 8	Week 24	Week 48
PIN		X	X	X
HAT-QoL	X		X	X
HIVTSQs	X		X	X
HIVTSQc				X
ACCEPT	X		X	X
Preference				X

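### The supportive Week 48 HIVTSQc comparison is the only between-arm health-outcome model in SAP Section 12.5.1 without a reference score; adding the Day 1 HIVTSQs total may gain some precision at little cost

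*SAP*

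**What the plan says.** SAP Section 2.2 lists treatment satisfaction change by HIVTSQc at Week 48 among the secondary endpoints. Section 12.5.1 fixes the between-arm model: "An analysis of variance (ANOVA) model will be used with covariates: treatment, age (<50, ≥ 50 years old), prior exposure to CAB+RPV", plus sex at birth and race. The data are observed cases: "The observed case (OC) dataset uses only the data that is available at Week 48, with no imputation for missing values". On its standing the section says: "No adjustment for multiplicity will be applied as these analyses will be considered supportive". The results are displayed separately for participants from Q4W ATLAS (Table 6.29) and from SOC (Table 6.30).

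For HIVTSQs, ACCEPT and HAT-QoL in participants with prior exposure, the same section ends its covariate list with "sex at birth, race (i.e. white, non-white) and baseline score value (as a continuous variable"). The matching sentence for participants without prior exposure also names a baseline score, although it attaches that score to unspecified other endpoints. The PIN model uses the Week 8 PIN score.

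Section 15.3.4.1 says: "Baseline is not applicable for PIN, HIVTSQc and Preference assessments". It defines baseline for the remaining questionnaires as the last value up to and "including the Maintenance treatment start date (expected to be collected at Day 1"), and its Table 12 schedules HIVTSQs at Day 1, Week 24 and Week 48. Section 5.2 provides that, unless otherwise stated, "if baseline data is missing no derivation will be performed and baseline will be set to missing".

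**The concern.** HIVTSQc asks participants to report improvement or deterioration in satisfaction (Section 15.6.6). How satisfied someone was on entering the trial is a natural predictor of that answer: a participant who was already very satisfied has less room to report improvement. The trial schedules a measurement of that level with the sister instrument, whose total is also built from items 1 to 11, and the HIVTSQc model does not use it.

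What is at stake is the width of the confidence interval for the Week 48 Q8W minus Q4W difference in Tables 6.29 and 6.30, and the chance imbalance in entry satisfaction that stays in the point estimate. No primary or key secondary conclusion depends on this comparison.

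**Working it through.** **1. Reference score in each between-arm model of Section 12.5.1**

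| Endpoint | Reference score in the model |
|---|---|
| HIVTSQs, ACCEPT, HAT-QoL | baseline score |
| PIN | Week 8 PIN score |
| HIVTSQc | none |

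The remaining PIN analysis is a within-participant signed-rank test, so it does not bear on the comparison.

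**2. Is the Day 1 HIVTSQs score a legitimate covariate?** Table 12 schedules it for Day 1. The footnotes to the schedule in Section 15.2.2 place the questionnaires at the start of the visit, ahead of the suicidality scale, and place that scale before randomization on Day 1. The score is therefore planned to precede allocation as well as treatment.

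**3. Does prior exposure already do the work?** For Table 6.29, probably little. Participants from ATLAS must have reached ATLAS Week 52 before randomization (Section 15.2.2, footnote a), so nearly all those from its Q4W arm should fall in the category above 24 weeks. This is an inference. The SAP does not give the distribution of prior exposure in either table.

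**4. Possible gain.** The SAP states no SD, correlation, power or precision for HIVTSQc, so there is no figure to reproduce. Let ρ be the within-arm partial correlation of Day 1 HIVTSQs with Week 48 HIVTSQc, given the covariates already in the model. Adding the score multiplies the residual variance by 1 − ρ², so

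SE ratio = √(1 − ρ²), and equivalent extra participants = 1/(1 − ρ²) − 1.

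| ρ (assumed) | SE ratio | CI narrower by | Equivalent extra participants |
|---|---|---|---|
| 0 | 1.000 | 0% | 0% |
| 0.1 | 0.995 | 0.5% | 1.0% |
| 0.2 | 0.980 | 2.0% | 4.2% |
| 0.3 | 0.954 | 4.6% | 9.9% |
| 0.4 | 0.917 | 8.3% | 19.0% |

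The ratio does not depend on sample size. For scale, with the full 510 per arm the SE without the covariate is √(2/510) = 0.0626 SD. With it the SE is 0.0623, 0.0614, 0.0597 and 0.0574 SD for ρ = 0.1 to 0.4. Power for a difference of 0.175 SD, which is 80% without the covariate, becomes 80.4%, 81.6%, 83.6% and 86.4%. Each of the two tables has fewer participants than this, so its intervals are wider throughout.

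**5. Bias.** In 2,000 simulated trials of 510 per arm with no true difference, the mean estimate was within 0.002 SD of zero under both models. The simulated SE ratios were 1.00 at ρ = 0 and 0.95 at ρ = 0.3, in line with the formula.

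**6. Missing Day 1 scores.** Suppose a fraction m, unrelated to outcome, lacks the score.

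- If those participants drop out of the model, variance is multiplied by (1 − ρ²)/(1 − m). The gain is cancelled when ρ² = m: ρ = √0.02 = 0.14 at 2% missing, and √0.05 = 0.22 at 5% missing.
- If the missing score is set to the mean, the multiplier is about 1 − (1 − m)ρ². At m = 5% and ρ = 0.3 the SE ratio is √(1 − 0.95 × 0.09) = 0.956, against √(0.91/0.95) = 0.979 if those participants are dropped.

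The SAP gives no missingness rate, so m is assumed.

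**The case against.** The strongest reply is that nothing here is wrong. The plan prespecifies a covariate-adjusted comparison of randomised arms. It is unbiased, its interval already allows for chance imbalance, and the section calls it supportive. The type I error-controlled satisfaction test is the one on HIVTSQs change from baseline. All of this stands, and it limits the point to a possible gain in efficiency.

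It can also be said that the other models adjust for their own instrument's score and HIVTSQc has none, so the plan is not inconsistent. That too is fair. A reader might infer that the other satisfaction models all use the Day 1 HIVTSQs score. Section 12.5.1 does not support this: ACCEPT and HAT-QoL are naturally read as using their own baselines, PIN uses Week 8, and only the HIVTSQs model would use the HIVTSQs baseline. But the statement that baseline is not applicable to HIVTSQc means only that it has no baseline of its own. It does not bar a related pre-treatment score as a covariate.

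Thirdly, the questionnaire text and the introductory wording of its three versions are not shown, so the period each version asks participants to compare with cannot be checked. This leaves the size of ρ open, including values near zero. It does not remove the plausibility of some association.

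Lastly, a Day 1 score is scheduled for all participants, which does not mean that all will supply one. Section 5.2 foresees missing baselines, and step 6 shows that dropping those participants could undo a small gain. The covariate is therefore worth adding only together with a rule for missing values.

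**Conclusion.** The point holds as a minor, optional improvement. The HIVTSQc model alone among the between-arm models of Section 12.5.1 lacks a reference score, and a suitable pre-treatment score is already scheduled. For assumed partial correlations from 0 to 0.4 the gain runs from nothing to about 8% of the interval width.

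A reader might go further and conclude that precision is certainly being lost, or that the estimate is distorted. The documents support neither. They give no correlation, so the loss may be negligible, and randomisation protects the comparison from bias whether or not the covariate is used.

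The figures assume a linear relation that is similar in both arms and Day 1 scores missing at random with respect to outcome.

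**What to change.** Before the Week 48 database freeze, amend the HIVTSQc entry in Section 12.5.1 as follows:

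- Add the Day 1 HIVTSQs total score as a continuous covariate.
- State that a missing Day 1 score is replaced by the mean, for covariate use only, as an exception to Section 5.2. Computing that mean over both arms within the population of each table keeps the rule independent of treatment. Week 48 HIVTSQc scores stay as observed.
- Keep the present ANOVA as a sensitivity analysis.

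The cost is one covariate, one missing-value rule and an extra display for each of Tables 6.29 and 6.30. No new data are needed, and the primary and key secondary tests are untouched.
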